Interest in Internet-based pain self-management	X		
Can walk one block?	X		
Consent Form	X		
Chart/Medication Review	X		X
WHYMPI-Interference Scale	X		X
Numeric Rating Scale of Pain Intensity (0-10)	X		X
Profile of Mood States	X		X
Beck Depression Inventory	X		X
Multidimensional Fatigue Scale	X		X
MOS Sleep Scale	X		X
Behavioral Goal Adherence		X	X
Patient Treatment Satisfaction Scale			X
Treatment Credibility Scale			X
Module(s) completed		X	
Usability of Module		X	
Time and content accessed		X	
Post-intervention Measure			X

In addition to completing assessments at baseline and 10-weeks post-baseline, participants will be contacted by the study staff via telephone on a weekly basis beginning 1 week post-baseline and ending at 10 weeks post-baseline. The brief phone contacts will serve to confirm continued Internet access to the VPMRC and to remind participants to continue to complete the VPMRC modules. Qualitative and quantitative feedback will be obtained. Questions will be asked on the following dimensions: goal adherence for previous week's goals (using a 0-10 Likert scale, where 0 indicates no adherence to completing the goal and 10 indicates complete adherence), feedback regarding usability of the previous week's module(s), and specific indication of modules most recently completed. The study staff member will also solicit questions about the content of the VPMRC and provide clarifying answers to these questions. Strict limits will be placed on the nature of the responses and length of time of the calls (i.e., no greater than 10 minutes).

Intervention Description (UC+VPMRC)

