pain self-management skills. Participants will be encouraged to complete the skill modules at their own pace. Participants will also be able to access other modules not identified by the self-assessment if they are interested in completing them. Participants will be provided with a pedometer at the baseline assessment to facilitate completion of the exercise/walking module, which requires patients to track the number of steps walked each day.

Attrition

The RA and study coordinator will monitor the study for attrition and follow-up with participants when they appear at risk for withdrawal or report the intent to withdraw. If a participant contacts the study coordinator to withdraw, s/he will first ask if there is a problem that s/he can address that would allow them to stay in the study. If not, s/he will ask subjects who wish to withdraw from treatment if they will consider continuing to complete the follow-up assessments. To keep losses-to-follow-up at a minimum, every effort, including reminder e-mails and follow-up phone calls, will be made to collect post-baseline data. We will also prospectively collect the reasons for missing data such as "patient refusal due to difficulty completing skill modules" or "patient moved away". Reasons for missing data will be evaluated during data analysis.

Outcome Measures

Standardized and reliable interview and questionnaire measures will be used to assess outcome and process variables. These outcome measures are similar to those we have used in prior CBT efficacy studies and are consistent with CONSORT and IMMPACT guidelines. In addition to these outcomes we also propose to examine treatment satisfaction, treatment credibility, and goal accomplishment.

Primary Outcome:

Pain Interference: The 9-item Interference subscale of the West Haven-Yale Multidimensional Pain Inventory (WHYMPI) assesses pain-related interference in social, work and household functioning and has demonstrated good internal consistency (0.86) and stability (0.85 over 2 weeks).²⁸ The WHYMPI-Interference Scale was recommended by IMMPACT as a core outcome measure for this domain.²⁹ A reduction in WHYMPI-Interference Scale scores of 0.6 or greater has been identified as an indicator of meaningful improvement in physical functioning and will be employed in this study.³⁰

Secondary Outcomes:

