Sleep Problems: Sleep problems will be assessed using the MOS Sleep Scale. The MOS is segregated into subscales addressing seven sleep domains (i.e. sleep disturbance, snoring, awaken short of breath or with headache, adequacy of sleep, somnolence, a problems index 1 and a problems index 2). An additional single item assesses quantity of sleep.³⁷

Behavioral Goal Adherence: Goal adherence for previous week's goals will be assessed via telephone on a weekly basis for 10 weeks post-baseline using a 0-10 Likert scale, where 0 indicates no adherence to completing the goal and 10 indicates complete adherence.

Tertiary outcomes:

Module completion: Participants will be asked during weekly (for 10 weeks) phone calls placed by the study staff about completion of modules (i.e., how many modules completed, which modules) during the previous week. In addition, the web developer will build a database to track time spent on each module, which modules were accessed, and number of times each participant accessed the program. This database will be linked only to userID and will not be linked with PHI.

Module usability: Participants will be asked during weekly phone calls about usability of modules. Specifically, they will be asked to rate each completed module on a 0-10 scale where 0= very difficult and 10=very easy, in terms of accessing information presented, understanding information presented, setting a module goal, navigating the module.

Treatment credibility: Participants' judgments of treatment credibility will be assessed at the post-baseline assessment interval using a questionnaire adapted from Borkovec and Nau.³⁸ This measure has been shown to have an internal consistency of .85 and test-retest reliability of .83.

Patient satisfaction: Patient satisfaction will be assessed by the Pain Treatment Satisfaction Scale which is a 5-item satisfaction survey designed to assess patient satisfaction with 5 domains of pain care.³⁹ This measure shows good internal consistency (.83-.90 across two samples) and significant associations to follow-up treatment satisfaction and staff and patient ratings of patient improvement.

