VPMRC program-specific feedback: Participants will be administered an investigator-created measure designed to assess the layout of the website, ease of navigation, relevance of the materials presented, appeal of the program, understanding of key concepts, appropriateness of the graphics and multimedia interface, ease of use, problems encountered, amount of material presented, and general likes and dislikes

Sociodemographic status and pain-relevant variables: Participants' age, sex, education level, racial/ethnic background, and marital status will be assessed at the time of the baseline examination. Pain-specific factors such as pain duration, number and location of pain sites, past and current pain treatments, cause of pain, and presence of radicular symptoms, will also be assessed at baseline.

Pain medication: At baseline, medication use will be assessed by the study coordinator through participant interview and VACHS computer pharmacy records. Medications will be coded into several categories, namely non-steroidal anti-inflammatory, non-opioid analgesics, opioid analgesics, and benzodiazepines and other sedative/hypnotics using a recording sheet used in our prior studies. The specific medication used, its dose, and schedule of administration will be recorded. At 10 weeks post-baseline, this information will again be collected via patient self-report using Trial DB, and participants' medical records will be independently reviewed for changes in medication regimen from baseline by the RA for corroboration.

Analytic Plan

Because the overall goal of the project is to develop a pain self-management resource for Veterans, the VPMRC, we will employ an iterative process of formative evaluation through two distinct Phases in order to optimally revise and modify the VPMRC. All analyses will be conducted in the service of further refining and optimizing the usability and effectiveness of the program. Ultimately, these data and the subsequent modifications to the VPMRC will produce a resource that can be submitted to examination of efficacy through a randomized controlled trial.

Phase I: Development of the VPMRC

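### The 0-10 module usability rating is taken only for completed modules, so mean usability is likely too high if people stop modules because they are hard to use

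*Combined protocol and SAP*

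**What the plan says.** All references are to the combined protocol and SAP.

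- **Outcome Measures, Tertiary outcomes, Module usability.** On the weekly calls, "they will be asked to rate each completed module on a 0-10 scale", with higher scores meaning easier. Four aspects are rated: accessing the information, understanding it, setting a goal and navigating. What counts as completed is not defined.
- **Phase II, Procedures (text after Table 4).** The same calls collect "feedback regarding usability of the previous week's module(s), and specific indication of modules most recently completed". Usability and completion appear as separate questions, and the section adds that "Qualitative and quantitative feedback will be obtained". Table 4 lists module usability as a weekly item without a completion condition.
- **Tertiary outcomes, Module completion.** A database will "track time spent on each module, which modules were accessed, and number of times each participant accessed the program". It is linked to userID only.
- **Tertiary outcomes, VPMRC program-specific feedback.** The Post-intervention Measure, given at 10 weeks, covers topics including "appropriateness of the graphics and multimedia interface, ease of use, problems encountered, amount of material presented, and general likes and dislikes". It does not depend on having finished any module.
- **Intervention Description.** "Participants will be encouraged to complete the skill modules at their own pace". Participants may also open modules that their self-assessment did not select.
- **Analytic Plan, Phase II.** Usability is summarized descriptively. Weekly-call data and the Post-intervention Measure are used to modify the program. The plan also says that tertiary usability data are collected only at 10 weeks, which does not fit the weekly collection described elsewhere.

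**The concern.** The four rated aspects are all plausible reasons for leaving a module part-way. If only finished modules are scored, whether a score exists can depend on the quantity the score measures. A participant defeated by poor navigation contributes nothing to the navigation mean for that module.

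The plan itself foresees the mechanism: the Attrition section gives difficulty with the skill modules as an example of a reason for missing data. It records this for the participant, not as a module rating. Self-paced use makes partly finished modules likely.

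Usability is part of the stated primary aim of Phase II, beside preliminary efficacy and satisfaction. The Analytic Plan says that all analyses serve refinement of the program ahead of a randomized trial. A flattering usability mean could therefore steer revision effort away from a module that needs it.

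**Working it through.** The plan states no usability target, standard deviation, completion rate or power, so there is no figure to reproduce. The check is on direction, and then on size under assumptions.

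**Direction.** Let R be the rating a participant would give a module they opened, and p the probability that they complete it. Then

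mean(R given completed) − mean(R) = Cov(R, p) / mean(p).

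The difference is positive only if completion rises with ease. It is zero if the two are unrelated, and negative if harder modules are completed more often.

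**Illustration 1: two kinds of module (all inputs assumed).** Of the modules opened, 30% are hard and would score 3; 70% are easy and would score 8. The mean over all opened is 0.3×3 + 0.7×8 = 6.50.

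| Completion, hard / easy | Mean over completed only | Excess |
|---|---|---|
| 30% / 90% | (0.09×3 + 0.63×8) / 0.72 = 5.31 / 0.72 = 7.38 | +0.88 |
| 60% / 90% | (0.18×3 + 0.63×8) / 0.81 = 5.58 / 0.81 = 6.89 | +0.39 |
| 80% / 80% | (0.24×3 + 0.56×8) / 0.80 = 5.20 / 0.80 = 6.50 | 0 |

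The identity agrees. In the first row, Cov(R, p) = 5.31 − 6.50×0.72 = 0.63, and 0.63 / 0.72 = 0.875.

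**Illustration 2: graded ease (all inputs assumed).** Ease has mean 5 or 7 and SD 2, rounded and clipped to 0-10. The log-odds of completion change by b per SD of ease. The ranges below cover both means.

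| Overall completion | b = −0.5 | b = 0 | b = 0.5 | b = 1.0 |
|---|---|---|---|---|
| 90% | −0.10 to −0.08 | 0 | +0.09 to +0.10 | +0.18 |
| 70% | −0.28 to −0.26 | 0 | +0.27 to +0.28 | +0.49 to +0.51 |
| 50% | −0.47 to −0.43 | 0 | +0.43 to +0.47 | +0.77 to +0.83 |

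**An extreme case (assumed).** Suppose 40 people open a module, 25 finish it and rate it 8, and the 15 who stop would all have rated it 3. The plan would report 8.0; the mean over all openers is (25×8 + 15×3)/40 = 6.125. This gap of 1.875 arises only because every person who stops is assumed to have found the module hard.

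**Can the other data recover the missing scores?**

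- The log shows that a module was opened and for how long, not whether it was hard, irrelevant or postponed.
- Completion reports show which modules were finished, not why others were left.
- The Post-intervention Measure asks about ease of use and problems, but once, at 10 weeks, and mainly at program level. It is missing for participants who have left.
- No analysis step links abandonment to the usability scores.

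**The case against.** The strongest reply is that the plan does not rest on this one item.

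- The Procedures text asks about the previous week's modules without requiring completion and says the feedback is partly quantitative, so callers could well collect scores on unfinished modules.
- Phase I has 15 Veterans work through the modules under observation, and changes are made before Phase II. That step is not selected on unsupervised completion.
- Abandonment is visible: the log records access and time, and the Analytic Plan uses reported completion and satisfaction to pick less-preferred modules for enhancement.
- Modules may be left for lack of relevance, interest or time, and one unfinished at one call may be finished and rated later.
- The outcome is tertiary and descriptive, and no test depends on it.

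Much of this stands. A reader might infer that hard modules are never rated, that the reported scores are biased upward as a matter of fact, or that the worst modules will show the most favorable ratings. The documents support none of these. Another participant may finish and score the same module; the Procedures wording is broader than the outcome definition; upward bias needs completion to rise with ease, which nothing here establishes; and even where selection raises a hard module's mean, nothing shows that it would overtake an easier one.

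The gap itself remains. The Module usability entry is the only place that says how the 0-10 score is obtained, and it is limited to completed modules. Phase I concerns supervised use of a version that is then modified. Low completion is read in the plan as a sign of preference, which does not separate a dull module from an unusable one.

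**Conclusion.** The point holds in a limited form. As defined under Tertiary outcomes, the 0-10 score omits modules opened and not finished, and the Procedures section describes the same call differently. Mean usability is likely biased upward if stopping is related to difficulty, and unbiased if it is not. The documents do not allow the size to be estimated. Under the assumed graded model with b between 0.5 and 1.0, it runs from about 0.1 points at 90% completion to 0.8 at 50%.

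The primary and secondary analyses are untouched. The change is still worth making, because the rating guides program revision and neither the missing scores nor the reasons for stopping can be recovered reliably afterwards.

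**What to change.** 1. Reconcile the two sections by changing the unit rated from each completed module to 'each module opened, whether or not completed', and define completion. Align the Analytic Plan's statement on the timing of tertiary data collection.
2. Identify opened modules by participant report on the call, and check them later against the userID-linked log. The documents do not describe callers having live access to the log, so the call should not depend on it.
3. Rate each module once: at completion, or when the participant reports having stopped. This avoids repeat ratings of a module opened over several weeks.
4. Allow 'not reached' for each aspect. Goal setting is the last of the four components listed for a module, so someone who stops early may have nothing to rate.
5. Add one item on the reason for stopping.
6. Report ratings for all openers and split by completion, beside the number of participants who accessed and who completed each module.

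The cost is a revised call script and a few extra items, which must fit within the 10-minute cap alongside goal adherence, completion and participants' questions. The change removes selection on completion only; participants who cannot be reached by telephone will still give no rating.

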The primary aim of this phase of the project is to execute a pilot feasibility trial to evaluate the preliminary efficacy of, usability of, and satisfaction with the VPMRC. A single treatment condition (Usual Care [UC] plus VPMRC) X two evaluation periods (baseline and 10 weeks post-baseline) design with multiple dependent measures will be employed. Participants in the study will be 55 Veterans with CLBP. Participants will continue to receive care as usual from their primary care providers (PCPs) and other healthcare providers.

Recruitment

VistA Search: We will identify potential Veterans for inclusion from available electronic medical record (EMR) data in VistA. All Veterans 18 years or older from VACHS (Station 689) with low back pain defined using the *International Classification of Diseases, Ninth Revision* diagnostic codes related to low back pain (724, 7240x, 7241x, 7242x, 7243x, 7244x, 7245x, 7246x, 7247x, 8460x, and 8472x) will be considered eligible. We will attempt to oversample OEF/OIF/OND, female, and minority Veterans, as these Veterans have high prevalence rates of chronic musculoskeletal pain conditions and are of particular interest in the context of the proposed study. We will then identify Veterans in this group to exclude psychiatric hospital admissions in the previous 30 days, suicide flag in the Electronic Medical Record (EMR), or behavioral alert flag in the EMR.

A letter will be sent to the identified Veterans from their PCPs informing them about the study and inviting them to participate. Veterans will be provided with information about the voluntary nature of the study and the option to "opt out" from further contact with study staff by notifying us of their lack of interest by phone, email or letter. Veterans who do not contact us will be called by the study RA to be further informed about the study and, if interested, to be screened for participation. Screening will include several of the key eligibility criteria for the study (e.g., confirmation of presence of CLBP, readiness to engage in self-management for pain, interest in Internet-based pain care, and absence of medical and psychiatric comorbidities). If screening suggests potential eligibility, and if the Veteran is interested, an in-person appointment for obtaining written informed consent and baseline assessment data will be scheduled. Solicitation letters will be mailed in waves in order to prevent overwhelming our capacity to offer participation in a timely manner.

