We will analyze the primary and secondary hypotheses according to the Intent-to-Treat principle. If missing data are minimal (e.g., <5%), we will conduct a complete case analysis; otherwise, imputation methods will be used to fill in the missing values. Several imputation approaches will be considered after inspection of the missing data rates and before any analyses of treatment effects are conducted. These approaches would include imputing the worst and best value (i.e., bounds on the treatment effects) and using multiple imputation assuming missing at random. These approaches would be supplemented by sensitivity analyses assuming nonignorable missingness. Only pre-specified baseline variables that may affect the outcome will be considered as adjustment variables in a sensitivity analysis. These variables include age, race/ethnicity, gender, educational attainment, and depressive symptom severity.

The primary endpoint is the mean difference in baseline to post-baseline follow-up scores on the primary measure of pain interference (i.e., WHYMPI-Interference Scale) at 10 weeks post-baseline. T-tests will be utilized to evaluate the effect of treatment on the primary outcome, and an ordinary least squares regression model will be used to control for potential confounders. The treatment will be represented by an indicator variable. The model fit will be assessed using graphical techniques and regression diagnostics. In a sensitivity analysis, we will examine the effect of treatment adjusted for the pre-specified set of baseline covariates. Analyses of covariance (ANCOVAs) will be employed to control for differences among participants in baseline scores and to determine whether participant characteristics are associated with changes in scores on outcome variables across time.

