Because the primary and secondary hypotheses test differences in outcome measure scores across time, we will use paired t-tests, or their non-parametric analogs (e.g., Mann-Whitney test) to compare mean (or median) scores on the outcomes across time. Given the multiplicity of tests for secondary outcomes (i.e., six outcomes) and the power of the study, in addition to maximizing sample size, we will use the Bonferroni procedure p-value, which we conservatively estimate to be $p = 0.008$, based on an overall significance of $p = 0.05/6$, to account for the number of comparisons. Our six secondary outcomes will be examined with the purpose of informing future modifications to the VPMRC and additional hypothesis generation. We have not grouped within subsets in order to ensure a more conservative approach. Tertiary hypotheses will examine data related to usability (use of and functionality) and satisfaction (satisfaction, credibility) with the VPMRC and will be collected only at 10 weeks post-baseline. Descriptive statistics will be employed to examine these data in order to describe participants' experiences with the VPMRC.

As in Phase I, quantitative data from the Post-intervention Measure with added data from the weekly phone calls for Phase II regarding usability of and satisfaction with the VPMRC will be used to modify the program. In addition, we will use specific primary and secondary outcomes data to inform modification of the VPMRC. For instance, if the data suggest a significant reduction in pain interference, but more modest changes in fatigue or depression, specific modules, such as Pacing (the pleasant activity scheduling coping skill) or Adaptive Stress Response (the using positive coping statements coping skill) will be targeted for further content and presentation enhancement to increase benefit to patients on these important related outcomes. We will also use data from tertiary outcomes to further modify presentation of the various treatment modules. For example, if certain modules are clearly preferred, as indicated by participant report of modules completed and satisfaction with the modules, other, less-preferred modules may be further enhanced (e.g., changes to audio-visual aspects, presentation of content within modules) to increase use, interest, and satisfaction.

6. References:

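### With one treatment condition, the planned OLS model with a treatment indicator cannot give the confounder-controlled treatment effect it is meant to give

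*Combined protocol and SAP*

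**What the plan says.** The Phase II Design section sets out "A single treatment condition (Usual Care [UC] plus VPMRC) X two evaluation periods (baseline and 10 weeks post-baseline) design". It adds that "Participants in the study will be 55 Veterans with CLBP". All of them keep their usual care and all get the program, so there is no comparator.

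For the primary outcome, the Analytic Plan (Phase II: Pilot Feasibility Trial of VPMRC) names t-tests of the treatment effect and says that "an ordinary least squares regression model will be used to control for potential confounders". The next sentence is "The treatment will be represented by an indicator variable". It continues: "In a sensitivity analysis, we will examine the effect of treatment adjusted for the pre-specified set of baseline covariates". The five listed covariates are age, race/ethnicity, gender, education and depressive symptom severity. A separate sentence plans ANCOVA for baseline scores and for characteristics associated with change.

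On missing data, if little is missing "we will conduct a complete case analysis; otherwise, imputation methods will be used to fill in the missing values".

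The following paragraph describes the test differently: "Because the primary and secondary hypotheses test differences in outcome measure scores across time, we will use paired t-tests".

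**The concern.** The regression wording is that of a two-arm comparison. An indicator needs a zero level, and the plan defines none. It also does not say whether the regression has one row per participant or one row per visit.

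What is at stake is interpretation and, in some forms, the error rate. A pilot report with a treatment effect adjusted for baseline covariates would look like confounder-controlled evidence. In this design it would be either impossible to compute or the raw pre-post change under another name. The plan expects these data to lead to a randomized trial, so a mislabelled effect could be carried into its planning.

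**Working it through.** **Inputs.** From the documents: one condition, two visits, n = 55, five covariates. The only correlation given for the primary scale is its stability of 0.85 over 2 weeks (Outcome Measures, Primary Outcome). The documents give no 10-week correlation (rho), no share of score variance explained by the covariates (R2), no SD, and no alpha for the primary test. Assumed here: rho 0.3 to 0.85, R2 = 0.2, equal variances at both visits, two-sided 5%. The plan has no figure of its own to reproduce on this point.

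**1. One row per participant.** Intercept, indicator and five covariates (one column each) make 7 columns. The indicator equals the intercept column, so the rank is 6. The coefficient is not estimable, and there is no error rate to discuss. Coding a covariate with more columns does not change this.

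**2. Stacked visits, complete pairs, indicator = visit.** Baseline covariates take the same value in both rows of a participant, so they are orthogonal to visit. The coefficient is therefore the raw mean change whatever is added. In simulation the largest gap was below 6e-15. No confounding is removed.

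**3. Standard error of that coefficient, listed covariates only.**
- Stacked OLS: SD × sqrt(2(1 − R2)/n).
- Paired: SD × sqrt(2(1 − rho)/n).
- Ratio: sqrt((1 − R2)/(1 − rho)). At rho = 0.5 and R2 = 0.2 this is sqrt(0.8/0.5) = 1.26.
- 95% CI half-widths in that case: t(103) × sqrt(1.6/55) = 0.338 SD, against t(54) × sqrt(1/55) = 0.270 SD paired.

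**4. Standard error if the outcome's own baseline is also a covariate.** Over the stacked rows the baseline score has slope (1 + rho)/2, so R2 = ((1 + rho)/2)². Then 1 − R2 = (1 − rho)(3 + rho)/4, and the ratio in step 3 becomes sqrt((3 + rho)/4). This is below 1 for every rho < 1, so the standard error is too small.

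**5. Type I error for no mean change.** Simulated with n = 55, 6000 replicates per cell and one covariate explaining 20% of variance:

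| rho | SE ratio, listed covariates | Type I error | SE ratio, own baseline | Type I error, own baseline | Own baseline + covariate | Paired t-test |
|---|---|---|---|---|---|---|
| 0.3 | 1.07 | 3.1% | 0.908 | 7.6% | 8.4% | 4.6% |
| 0.5 | 1.26 | 1.7% | 0.935 | 7.0% | 7.4% | 4.9% |
| 0.7 | 1.63 | 0.2% | 0.962 | 6.1% | 6.3% | 5.2% |
| 0.85 | 2.31 | 0.0% | 0.981 | 5.7% | 5.7% | 5.0% |

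Further runs over the same rho range at R2 = 0.2 gave 0.0% to 4.3% with the listed covariates and 5.7% to 8.8% with the own baseline added.

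**6. Treatment against time.** Suppose the program has no effect but scores drift by 0.3 points, half the 0.6-point threshold that the protocol calls meaningful. With assumed SD 1.0 to 1.5 and rho 0.5 to 0.85, the paired t-test then rejects in 31% to 98% of trials. It correctly detects a mean change; it cannot say what caused it.

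**The case against.** **Treatment may simply mean time.** This is the kindest reading, and the paragraph on paired t-tests supports it. It makes the coefficient estimable, but the claim to control confounders still fails by step 2. Other estimable forms exist (no intercept with centred covariates, or participant terms). The plan specifies neither, and with complete pairs both return the raw mean change.

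**Pairs may be incomplete.** If incomplete pairs were stacked as available rows, adjustment could move the estimate. The missing-data rule points the other way: complete cases when little is missing, imputation otherwise. The 5% in that rule is only an example, so it is not a fixed cut-off.

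**Adjustment can be useful.** This stands. With 11 of 55 lost through covariate-related dropout (assumed rho about 0.7) and a covariate explaining 10%, 20% or 30% of change variance, the completers' paired mean was biased by −0.06, −0.08 and −0.11 SD. Regressing change on covariates centred at the enrolled-sample mean was unbiased (within 0.005). A covariate-adjusted pre-post change is therefore legitimate, and deleting all adjustment would go too far.

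**The error may look harmless.** A reader might infer from step 3 that it only widens intervals and cannot produce a false claim of benefit. The documents do not support that in general. It holds for the primary outcome in a stacked model with the five listed covariates and positive residual correlation, since baseline pain interference is not on the list. It has no meaning when nothing can be estimated. It reverses if the own baseline enters, for example if the model is extended to the BDI with baseline BDI as the depressive-severity covariate. The plan assigns baseline scores to ANCOVA, so the reversal is possible but not prescribed. Drift or regression to the mean can also favour the program if the coefficient is read as a treatment effect.

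**Conclusion.** The point holds. The treatment-indicator model is wrong as written, beyond being under-described: in a one-condition design it is either not estimable or, with complete pairs, the raw mean change with a standard error that ignores pairing. The direction of the standard-error problem depends on which covariates enter, and its size rests on the assumed rho and R2. The structural result needs neither.

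Two stronger inferences are not supported. One is that the primary analysis fails: the paired t-test is a valid test of no mean change, with simulated type I error of 4.6% to 5.2%. The other is that the paired t-test is wholly untouched: the plan gives the t-tests the same treatment-effect target, and they cannot meet it either.

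Severity is low to moderate. The model is supplementary, and the plan says of this formative work that "All analyses will be conducted in the service of further refining and optimizing the usability and effectiveness of the program".

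**What to change.** In the Phase II Analytic Plan:

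1. Drop the treatment indicator, or define it as visit.
2. Replace the treatment-effect and confounder-control wording with mean change from baseline to 10 weeks.
3. State that the t-tests are the paired t-tests of the following paragraph, with the paired mean change and its 95% CI as the primary estimate.
4. Keep the covariate sensitivity analysis only as an adjusted pre-post change from a model that respects pairing, for example visit with a within-participant covariance. Say that with complete pairs such a model with baseline covariates returns the paired mean change, so it can differ only when 10-week scores are missing.
5. If change is instead regressed on centred covariates, do not report the default intercept standard error as that of the mean change. It is too small when covariates predict change (simulated type I error 6.5%, 8.0% and 9.9% when they explain 10%, 20% and 30% of change variance).
6. Keep the regression or ANCOVA of change on baseline characteristics as an exploratory analysis of predictors of change.

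The cost is a wording change to the analysis plan, with no new data or participants. The downside is that no adjusted treatment effect is reported, which this design could not supply in any case.
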